1.0 Objectives*

1.1 The purpose of our research is to compare the effectiveness of 40mg/ml sodium thiosulfate (STS) solution to normal saline (0.9% sodium chloride) when injected intralesionally for the treatment of calcinosis cutis. Our specific aim is to assess the response of dystrophic and idiopathic calcinosis cutis to the injections of sodium thiosulfate in our patients.

1.2 Our hypothesis is that three injections of STS, each spaced one month apart, will significantly improve our patients' calcinosis cutis condition to a point where they are effectively clear or have a 2-point improvement in their Physician Global Assessment (PGA) scores when compared to normal saline.

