7.0 Study Timelines*

7.1 Subjects are expected to participate in this study for a total of three months. During these three months, subjects will be required to come to UCF Health Clinic at [name] for a total of four appointments:

- Timeline:
 - Week 0 (Visit 1): 90 minutes
 - 48-hour post-treatment follow-up phone call: 5 minutes
 - Week 4 (Visit 2): 90 minutes
 - Week 8 (Visit 3): 90 minutes
 - Week 12 (Visit 4): 15 minutes
- Ten months is the anticipated length of time to recruit subjects
- The study is expected to be completed by April 2019.

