8.0 Study Endpoints*

8.1 Study endpoints:

- Primary:
 - Change in size of study lesions
 - Change in Physician Global Assessment
 - Visual Analog Scale of pain of injection
- Secondary:
 - Adverse Events

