- During each visit subjects will be monitored for any adverse events and asked about any potential adverse events since the last visit. Any adverse events will be logged on the Adverse Events Form (see attached).
- Visit 1 will be followed with a 48-hour post-treatment phone call to assess for any adverse events.
- After all subjects have completed their participation, photographs of lesions will be reviewed by [name] who will fill out the Independent Observer Case Report Form (see attached) for each visit. He will be blinded as to which lesions received which treatment and at which visit in the study the lesions were photographed.
- Screening and consent
 - First, each subject will sit down with the principal investigator to discuss the study in depth and review the screening criteria. After all risks, benefits, alternatives, and questions have been discussed consent will be obtained.
 - After the informed consent form is signed, the eligibility screening portion of the case report form will then be filled out by the principal investigator with the research subject. If necessary, a pregnancy test will be performed.

A Comparative Study of the Efficacy of Intralesional Sodium Thiosulfate Versus Intralesional Normal Saline for the Treatment of Dystrophic and Idiopathic Calcinosis Cutis, A Double-Blind Randomized Placebo-Controlled Trial

- Solution preparation
 - 50 ml vials of sodium thiosulfate (250mg/ml) will be used for preparation of the treatment solution.
 - The solution from the bottle will be diluted in a ratio of 1 part sodium thiosulfate 250mg/ml to 5.25 parts sterile water to yield a 40mg/ml solution of sodium thiosulfate.¹⁴ This is done to make the final solution as close to isotonic as possible.
 - 30 ml vials of sodium chloride 0.9% will be used for the control treatment.
 - The solutions will be drawn up in 1 cc syringes utilizing a 25g needle by [name]. The needle will then be replaced with a capped 30g ½ inch needle.
 - All solutions will be drawn up by [name] the day of use and discarded immediately after use.
 - Treatment and control will be randomized once for the entire study and all subjects based upon a one-time flip of a coin as follows:
 - If coin flip is heads: all “A” lesions will receive STS and all “B” lesions will receive normal saline
 - If coin flip is tails: all “A” lesions will receive normal saline and all “B” lesions will receive STS
 - This result will be recorded on the Unblinded Treatment Document (See attached).

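### The 48-hour adverse-event call follows only the first of three injection visits, so brief events after the second and third are captured less completely

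*Combined protocol and SAP*

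**What the plan says.** Section 1.2 sets out "three injections of STS, each spaced one month apart". Sections 7.1 and 9.2 place the injection visits at Weeks 0, 4 and 8, with a final assessment and no injection at Week 12.

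The phone contact appears once in the 7.1 schedule, between Visit 1 and Visit 2: "48-hour post-treatment follow-up phone call: 5 minutes". The later entries are "Week 4 (Visit 2): 90 minutes", "Week 8 (Visit 3): 90 minutes" and "Week 12 (Visit 4): 15 minutes", with no call between them. Section 9.2 also lists the call once, after the baseline visit, and then ties it to that visit in words: "Visit 1 will be followed with a 48-hour post-treatment phone call to assess for any adverse events".

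Otherwise, adverse events are collected at the visits: "During each visit subjects will be monitored for any adverse events and asked about any potential adverse events since the last visit". Each of the three injection visits includes an hour of monitoring (minutes 30 to 90). Both lesions are photographed and assessed at every visit, and section 9.3 gives subjects the principal investigator's phone number.

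Section 8.1 has a single secondary endpoint, "Adverse Events". Section 12.1 uses cumulative adverse-event data, comparing treated with control lesions, once 5 of 10 subjects have completed the study.

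**The concern.** The secondary endpoint is measured more closely after one injection than after the other two. After injection 1, someone asks about events within two days. After injections 2 and 3, nobody asks until the next monthly visit.

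The events exposed to this are those that start after the subject has left the clinic and resolve before the next visit. Several of the risks named in section 14.1 can be of this kind, such as nausea, headache, or discomfort at an injected site. With two lesions injected on the same day, a subject asked weeks later may also be less sure which one was affected, and the comparison in 12.1 depends on that attribution.

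Section 13 adds a smaller exposure. A subject may stop after any visit, and data collection then ends. Someone who leaves after Visit 2 or Visit 3 would have no scheduled post-clinic enquiry about that injection.

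At stake is the completeness of a small safety data set. No efficacy result, sample size or error rate is affected.

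**Working it through.** **Inputs**
- Injection visits per subject: 3 (1.2, 7.1, 9.2).
- 48-hour calls per subject: 1, after Visit 1 (7.1, 9.2).
- Visit lengths: 90, 90, 90 and 15 minutes; call length 5 minutes (7.1).
- Visit window: plus or minus 8 days at each follow-up (9.2).
- Eligible subjects: 10, from 12 enrolled (4.1, 23.2).
- Stated subject time: about 5 hours (26.1).

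**1. The plan's own time figure.** Visits take 90 + 90 + 90 + 15 = 285 minutes. With one call, 285 + 5 = 290 minutes; 290 / 60 = 4.83 hours, which agrees with the stated figure. With three calls, 285 + 3 × 5 = 300 minutes = 5.0 hours, which agrees equally well. So 26.1 does not show which call schedule was intended. The evidence for a single call is the text of 7.1 and 9.2, and both point the same way.

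**2. Share of injection visits without a call.** (3 − 1) / 3 = 66.7%. For 10 subjects this is 20 of 30 injection visits; if all 12 enrolled were treated, 24 of 36. At the 12.1 review, 5 completers contribute 5 × 3 = 15 injection visits, of which 5 × 2 = 10 had no call.

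**3. Time from an uncalled injection to the next scheduled contact.** Nominally 4 weeks = 28 days. The protocol does not say where the window is anchored:
- If it runs from the previous visit: 28 − 8 = 20 to 28 + 8 = 36 days.
- If both visits are timed from baseline, each can move by 8 days: 28 − 16 = 12 to 28 + 16 = 44 days.

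**4. Contact after each injection, side by side**

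| Period after injection | Visit 1 | Visits 2 and 3 |
|---|---|---|
| One-hour clinic monitoring | Observed | Observed |
| Clinic departure to 48 hours | Call at 48 hours | Recall at next visit, or unprompted phone call |
| 48 hours to next visit | Recall at next visit, or unprompted phone call | Recall at next visit, or unprompted phone call |
| Next visit | Lesions examined and photographed | Lesions examined and photographed |

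Only the second row differs. The unequal ascertainment is therefore mainly in the first two days after the subject leaves the clinic.

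**5. Cost of equal contact.** 2 calls × 5 minutes × 10 subjects = 100 minutes in total.

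**The case against.** The best defence is that the plan already has several safeguards, and that extra contact after first exposure followed by solicited reporting at every visit is a coherent design. Every injection is directly observed and followed by an hour of monitoring, so immediate reactions, including most vasovagal episodes and intolerance of injection pain (8.2), should be seen. A local reaction that persists will be visible on the labelled lesion at the next visit. Subjects can telephone in between. After Visit 1, too, anything later than 48 hours depends on recall. All of this stands, and it confines the point to brief events that start after clinic departure.

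A reader might infer four stronger things that the documents do not support:

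- **That all adverse events after two thirds of the injections rest on a month's recall.** The safeguards above rule this out.
- **That the comparison of sodium thiosulfate with saline is biased.** Both lesions are in the same subject and share the same contact schedule, so no direction of bias is shown.
- **That a falling event rate across injections would be misread as tolerance.** No such analysis is planned. Section 11.1 speaks generally of differences across times and does not name adverse events.
- **That the 12.1 rule is undermined.** It concerns severe events, which are the least likely to be forgotten. Some loss of sensitivity is possible, but the documents give no figure from which to estimate it.

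Nor can it be said that the affected lesion goes unrecorded. The Adverse Event Form is an attachment that is not reproduced and may already capture it; 12.1 presupposes that something does.

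These arguments limit the consequence but do not remove the asymmetry. Observation ends at one hour, the telephone route is passive, and the protocol gives no reason for making the call after one injection and not the others.

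**Conclusion.** The point holds as a minor limitation of safety ascertainment. Two of three injection visits (20 of 30 for 10 subjects) have no scheduled contact until the next visit, nominally 28 days later. Capture of the only secondary endpoint in 8.1 is therefore less complete after injections 2 and 3 than after injection 1, mainly between clinic departure and 48 hours and only for events gone by the next visit.

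The counts and times follow directly from the schedule, apart from the interval range, which depends on how the window is anchored. That brief events are more likely to be missed without the call is a judgement: the documents contain no reporting or recall rate, so the number of events lost cannot be estimated.

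**What to change.** Amend 7.1 and 9.2 so that the same 5-minute adverse-event call is made 48 hours after each of Visits 1, 2 and 3, with the same questions each time. For each event, note whether it concerns lesion A, lesion B or is systemic, if the Adverse Event Form does not already do so. The change concerns data collection only.

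The cost is two short calls per subject by existing staff, 100 minutes over 10 subjects. Section 26.1 needs no change, because 300 minutes still fits its stated time.

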9.2 Timeline

- Subject visits
 - The sodium thiosulfate and saline solution will be prepared the same day as the subject's baseline visit after consent to participate is obtained.
 - Baseline Visit
 - Minute 00-15:
 - Informed consent, HIPAA authorization, and screening and enrollment process.
 - Minute 15-30:
 - Obtain demographics and medical history via Demographics Form and Medical History Form (attached)
 - Selection of 2 lesions of dystrophic or idiopathic calcinosis cutis.
 - Note: The lesions must be at least 2mm in diameter and no larger than 2cm in diameter. If a lesion smaller than 2cm is not available then a 2 cm x 2 cm portion of a larger lesions will be used.
 - One lesion will be "Lesion A", and the other will be "Lesion B" for the entire study duration.
 - Lesions will be labeled with their corresponding letter 'A' and 'B' with a marker and photographed
 - Assessment of calcinosis cutis lesions via Case Report Form (see attached).
 - Administration of STS and normal saline.
 - Minute 30-90:
 - Monitoring of subject for adverse events
- 48-hour follow-up phone call:
 - Minute 0-5:
 - Brief phone call to assess for any adverse reactions

A Comparative Study of the Efficacy of Intralesional Sodium Thiosulfate Versus Intralesional Normal Saline for the Treatment of Dystrophic and Idiopathic Calcinosis Cutis, A Double-Blind Randomized Placebo-Controlled Trial

-
- 1-month (+/- 8 days) Follow-up
 - Minute 00-30:
 - Lesions will be labeled with their corresponding letter 'A' and 'B' with a marker and photographed
 - Assessment of calcinosis cutis via Case Report Form (attached)
 - Administration of STS and normal saline.
 - Minute 30-90:
 - Monitoring of subject for adverse events
 - Debrief of subject
- 2-month (+/- 8 days) Follow-up
 - Minute 00-30:
 - Lesions will be labeled with their corresponding letter 'A' and 'B' with a marker and photographed
 - Assessment of calcinosis cutis via Case Report Form (attached)
 - Administration of STS and normal saline
 - Minute 30-90:
 - Monitoring of subject for adverse events
 - Debrief of subject
- 3-month (+/- 8 days) Follow-up
 - Minute 00-15:
 - Lesions will be labeled with their corresponding letter 'A' and 'B' with a marker and photographed
 - Assessment of calcinosis cutis via Case Report Form (attached)

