 - [name] will not be notified of the result until after completion of the study so as to keep him blinded.
 - The syringes will be labeled with an “A” or “B” label for blinding by [name], or [name].

- Administration of study solutions
 - A volume of 0.1 ml/cm² of normal saline or STS will be injected into each lesion. Therefore, a maximum of 0.4ml of 40mg/ml STS or 16mg of STS (given maximum size of 2 cm x 2 cm) will be used per visit per subject.
 - The same treatment lesion will be injected only with STS every injection and the same control lesion will be injected only with normal saline (0.9% sodium chloride) every injection. In other words, “Lesion A” will always be injected with solution A and “Lesion B” will always be injected with solution B.
 - [name], a board-certified dermatologist, will be administering all injections of STS and normal saline to minimize risks for subjects.

- Disposal Protocol:
 - After use, needles will be disposed of in red sharps container according to UCF Health policy
 - After use, urine samples will be disposed of in the toilet according to UCF Health policy

A Comparative Study of the Efficacy of Intralesional Sodium Thiosulfate Versus Intralesional Normal Saline for the Treatment of Dystrophic and Idiopathic Calcinosis Cutis, A Double-Blind Randomized Placebo-Controlled Trial

9.3 Risk Management:

- Subjects will be directly observed during the administration of the STS and normal saline for any adverse events. An anaphylaxis kit is available in clinic should any subject experience such an event. The principal investigator is certified in basic cardiopulmonary life support and an AED is present in the facility. Subjects will be provided with the phone number of the PI should any issues related to participation in the study arise.
- Sodium thiosulfate is currently FDA-approved for as an antidote in the treatment of cyanide poisoning. FDA phase III studies are currently being conducted for use in calciphylaxis.
- 0.9% Sodium chloride is currently FDA-approved for parenteral replenishment of fluid, diluting or dissolving drugs for intravenous, intramuscular or subcutaneous injection, according to instructions of the manufacturer of the drug to be administered.
- Sterile water is currently FDA-approved as a solvent or diluent vehicle for parenterally administered drugs or solutions and as a source of water for parenteral fluid replenishment after suitable additives are introduced.

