11.0 Data Management* and Confidentiality

11.1 Data will be reported descriptively [mean and standard deviation; median (min-max) and frequency and percentage]. Interrater reliability of PGA will be conducted using Cohen's kappa statistic. As a second step, differences across times and between groups will be explored with non-parametric tests, such as Kruskal-Wallis test and the Mann Whitney U test. Statistical significance will be tested at $p < .05$.

The data will be analyzed for significant differences with aid of a statistician. The results of the data analysis will be graphed for each parameter.

11.2 For our study, we will recruit up to 12 adult male and female volunteers ages 18 years and older. This number is estimated from clinical knowledge of the cases that present to treatment on an annual basis at the research site. Furthermore, a review of the existing literature suggests that the targeted sample size is commensurate to other published studies.^{3,4,13,5-12}

11.3 Data will be managed as follows:

- Data will be stored in the secure HIPAA-compliant database called REDCap.
- Unique identifiers will be created using sequential numbers (i.e. 1, 2, 4 etc.).
- No data collection instrument in REDCap will contain identifying information
- The Screening and Enrollment Log, Drug Accountability Log, Unblinded Treatment Document, Demographics Forms, Medical History Forms, Eligibility Forms Case Report Forms, Independent Observer Case Report Forms, Adverse

A Comparative Study of the Efficacy of Intralesional Sodium Thiosulfate Versus Intralesional Normal Saline for the Treatment of Dystrophic and Idiopathic Calcinosis Cutis, A Double-Blind Randomized Placebo-Controlled Trial

Event Forms (see attached documents) will all be stored in the regulatory binder in a locked drawer in a locked room at UCF Health. Only [name] will have access to this locked drawer.

- Photographs will be taken with a UCF Health digital camera. The photographs will then be transferred to a folder on a password protected HIPAA compliant network drive for clinical research at UCF Health. After transfer of photographs to clinical research folder they will be deleted from the camera. Photographs will be labeled with subject ID number and visits number (i.e Subject 01 3-month)

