12.0 Provisions to Monitor the Data to Ensure the Safety of Subjects*

12.1 The plan to periodically evaluate the data collected regarding both harms and benefits to determine whether subjects remain safe is as follows:

- The principal investigator and statistician will review cumulative adverse event data after 5 out of 10 subjects have completed the study.
- If there are more severe adverse events in the treatment lesions compared to the control lesions with $p < 0.05$ then the study will be suspended immediately.

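### One coin flip fixes the A/B code for every subject, so treatment cannot be separated from the lesion label and one disclosure reveals every allocation

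*Combined protocol and SAP*

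**What the plan says.** Section 9.2 (Solution preparation) sets the allocation: "Treatment and control will be randomized once for the entire study and all subjects based upon a one-time flip of a coin". On heads, "all “A” lesions will receive STS and all “B” lesions will receive normal saline"; on tails, the reverse. Under Administration of study solutions, the same section keeps each lesion on its lettered solution at every injection.

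The baseline visit in section 9.2 lists "Selection of 2 lesions of dystrophic or idiopathic calcinosis cutis", gives size limits, and says each letter is kept throughout. It does not say how the letters are assigned or who assigns them. At each visit, "Lesions will be labeled with their corresponding letter 'A' and 'B' with a marker and photographed".

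Two blinding safeguards are stated in section 9.2. One person "will not be notified of the result until after completion of the study so as to keep him blinded". Of the independent photograph reader the plan says: "He will be blinded as to which lesions received which treatment and at which visit in the study the lesions were photographed".

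Two other sections bear on the point. Section 11.1 plans "non-parametric tests, such as Kruskal-Wallis test and the Mann Whitney U test" at the .05 level. Section 12.1 has the principal investigator and the statistician review adverse events once 5 of 10 subjects have completed, with suspension "If there are more severe adverse events in the treatment lesions compared to the control lesions" at p < 0.05.

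**The concern.** STS lesion against saline lesion is the only controlled comparison in this trial. Randomising within each subject would spread any habit in choosing, labelling, injecting or scoring lesions across both treatments. A single flip for the whole study does not. If lesion A tends to be the more responsive site, or is always injected or scored first, that tendency falls on the same treatment in all subjects. A baseline size difference matters for the change endpoints only if size affects response.

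Blinding also has a single point of failure. Under one shared code, a disclosure about one subject is a disclosure about all. The section 12.1 comparison of treatment with control lesions is one possible route, because anyone who sees it by lesion letter then knows the code for subjects still to be treated. The photographs are a weaker route. Unless the letters are masked, which the plan does not mention, the reader sees the same letter for the same treatment in every subject.

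**Working it through.** **Inputs from the document.** One flip for the study (9.2); 12 enrolled to obtain 10 eligible subjects, with one lesion pair each (4.1, 9.2); significance at .05, sidedness not stated and taken here as two-sided (11.1); Mann-Whitney named as an example test (11.1). The plan gives no effect size, SD or power, so there is no figure of its own to reproduce.

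**Step 1: count the allocations.** One flip gives 2 possible allocations, whatever the number of subjects. One flip per subject gives 2^10 = 1,024 for 10 subjects, or 2^12 = 4,096 for 12. The smallest two-sided p-value a randomisation test can reach is 2/(number of allocations): 2/2 = 1.0 with one flip, and 2/1,024 = 0.002 with ten flips. The single flip alone therefore supports no significance statement. Any p-value must rest on assuming that A and B lesions are exchangeable.

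**Step 2: size of the bias.** Let b be the mean A-minus-B difference in response with no drug effect, in SDs of the within-subject difference. With one flip, the STS-minus-saline contrast is shifted by +b or -b, whatever the sample size. With a flip per subject, if k of 10 subjects have STS on A, the shift is b(2k - 10)/10. This averages zero and has SD b/√10 = 0.32b. With a balanced list (k = 5) the shift is exactly zero.

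**Step 3: effect on the tests.** I simulated trials of 10 subjects with normal outcomes and no drug effect, using exact two-sided .05 tests (40,000 trials per setting). Both b and the within-subject correlation r are assumptions. Rejection rates:

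| Test and allocation | b = 0 | b = 0.25 | b = 0.5 | b = 1.0 |
|---|---|---|---|---|
| Signed-rank, one flip | 5% | 11% | 28% | 79% |
| Signed-rank, flip per subject | 5% | 5% | 5% | 5% |
| Mann-Whitney, r = 0, one flip | 4.2% | 9.8% | 28.9% | 80.7% |
| Mann-Whitney, r = 0, flip per subject | 4% | 5% | 5% | 8% |
| Mann-Whitney, r = 0.3, one flip | 2.0% | 5.3% | 17.8% | 68.2% |
| Mann-Whitney, r = 0.5, one flip | 0.9% | 2.8% | 10.4% | 53.0% |
| Mann-Whitney, r = 0.5, flip per subject | 1% | 1% | 1% | 3% |
| Mann-Whitney, r = 0.7, one flip | 0.2% | 0.7% | 3.5% | 27.9% |

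A paired t test behaves like the signed-rank test (30% against 5% at b = 0.5). Mann-Whitney ignores the pairing, so it is conservative when r is positive; its rates should be read against its own b = 0 column.

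The flip is symmetric, so half of these rejections favour STS. At b = 0.5 that is 28/2 = 14% for signed-rank and 28.9/2 = about 14% for Mann-Whitney at r = 0, against a nominal 2.5% in that direction.

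**Step 4: more subjects.** The shift stays at b while the standard error falls as 1/√n, so the standardised shift b√n grows. At b = 0.5 it is 1.58, 2.24 and 3.16 for n = 10, 20 and 40. The one-flip signed-rank rate rises accordingly from 28% to 55% to 84%; with a flip per subject it stays at about 5%.

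**Step 5: disclosure.** With one flip, knowing one subject's allocation gives all 10 with certainty. With independent flips, the other 9 remain even chances, and the probability of guessing all of them is 0.5^9 = 0.002.

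**The case against.** The strongest reply is that harm requires A and B lesions to differ systematically in response, and nothing in the document shows that they do. The forms that might hold a labelling rule are attachments and are not reproduced. This stands: bias is possible, not proven, and with no A/B difference the error rates are not inflated.

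A fair flip also gives some protection. It randomises the direction of any A/B difference, so expected bias over the flip is zero. While the code is concealed, nobody can steer the better lesion to STS. That is true, but only one flip will ever be made. Once it is made, the full bias applies to every subject and does not average out.

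The simulated rates cover both directions, and at higher correlation the named Mann-Whitney test stays below 5% for modest differences (3.5% at r = 0.7, b = 0.5). Both points are right. The low rates reflect a test that wastes the pairing. They do not reflect protection from the design: the estimated effect is still shifted by the full b.

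Lesion size is recorded, so a recorded difference that varies across subjects could be partly adjusted for, though weakly with 10 pairs. A constant or unrecorded difference could not.

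The two unblinding routes are conditional. Section 12.1 does not say that letters are shown with treatment, and a photographed letter reveals nothing to someone without the code. These are secondary points, and the confounding does not depend on them.

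**Conclusion.** The concern holds and should be fixed before the first subject is labelled. Treatment is fully confounded with the A/B label, nothing in the document supplies subject-level randomisation or a neutral labelling rule, and one disclosure reveals all allocations. These conclusions need no assumption beyond the text.

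The size of the harm does rest on assumptions. For an A/B difference of 0.25 to 1.0 SD of the paired difference, a signed-rank test would reject falsely in 11% to 79% of trials. Mann-Whitney would do so in 9.8% to 80.7% at correlation 0, falling to 0.7% to 27.9% at correlation 0.7. A constant or unrecorded A/B difference cannot be removed after data collection, and the blinded photograph review does not remove it either.

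**What to change.** Replace the one-time flip with a separate allocation for each subject, made after that subject's two lesions have been chosen and labelled. Suggested wording for section 9.2: *For each subject, once lesions A and B have been labelled, the person who prepares the syringes flips a coin. Heads: A receives STS and B saline. Tails: the reverse. The result is recorded for that subject on the Unblinded Treatment Document and applies at all of that subject's visits.* The preparer keeps the codes and does not share them with anyone who labels, injects or scores lesions.

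A prepared list, five of each for 10 subjects, can replace the coin. Ten independent flips split 8:2 or more unevenly with probability 2 × (45 + 10 + 1)/1,024 = 11%, and a balanced list avoids that. The price is that an unadjusted paired test becomes conservative if A and B do differ (signed-rank about 3% at b = 0.5).

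The cost is a wording change, one line per subject on an existing form, and a code look-up at each visit with a small added risk of a mix-up. Baseline syringes must be labelled after the lesions are. Section 9.2 already has solutions prepared the same day after consent, so this order is workable. Whether existing staff can hold the codes cannot be judged, because names are removed.

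The section 12.1 review would then reveal only the subjects included in it. If its cumulative data cover subjects still under treatment, their codes would be exposed too. The letters would still appear in the photographs, but one letter would no longer mean one treatment across subjects.
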